2.4.4.4.2 VAS from SHAQ

Change in VAS from SHAQ from baseline to Week 24 and from baseline to Week 35 will be analyzed using the MMRM model described in [Section 2.4.4.4](#).

CDF graphs will be also presented for each VAS (percentage of patients according to the relative improvement from baseline in VAS) at Week 24 and Week 35.

2.4.4.4.3 UCLA SCTC GIT 2.0 score

Change in UCLA SCTC GIT 2.0 score from baseline to Week 24 and from baseline to Week 35 will be analyzed using the MMRM model described in [Section 2.4.4.4](#).

2.4.4.4.4 TJC28

Change in TJC28 from baseline to Week 24 and from baseline to Week 35 will be analyzed using the MMRM model described in [Section 2.4.4.4](#).

2.4.4.4.5 Digital ulcer count

Change in digital ulcer count (sum of active or new plus indeterminate/healing digital ulcers secondary to SSc) from baseline to Week 24 and from baseline to Week 35 will be analyzed using the MMRM model described in [Section 2.4.4.4](#).

The digital ulcer count, as well as the subcategories: number of active/new ulcers and number of indeterminate/healing ulcers, will also be descriptively summarized by treatment group and by time point.

2.4.4.4.6 EQ-5D-5L

Change in EQ-5D-5L (VAS and index) from baseline to Week 24 and from baseline to Week 35 will be analyzed using the MMRM model described in [Section 2.4.4.4](#). The EQ-5D-5L (index and VAS) will be summarized descriptively at each time point.

CDF graphs will be also presented for EQ-5D-5L index and EQ-5D-5L VAS (percentage of patients according to the relative improvement from baseline in EQ-5D-5L value [index or VAS]) at Week 24 and Week 35.

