Dressing & Grooming	Devices used for dressing (button hook, zipper pull, long handled shoe horn, etc.)
Arising	Built up or special chair
Eating	Built up or special utensils
Walking	Cane, walker, crutches, wheelchair
Hygiene	Raised toilet seat, bathtub seat, bathtub bar Long handled appliances in bathroom
Reach	Long handled appliances for reach
Grip	Jar opener (for jars previously opened)

The HAQ-DI composite score is calculated as the average of the scores of the domains. The patient must have a score for at least 6 of the 8 domains for the composite score to be calculated.

The HAQ-DI composite score is obtained by dividing the sum of the domains by the number of answered domains. This gives a score between 0 (no impairment in function) and 3 (maximal impairment of function).

If less than 6 domains have been scored then the HAQ-DI composite score is missing.

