- Change in EQ-5D-5L index from baseline to Week 24.

EQ-5D-5L (see [Appendix F](#)) is a generic measure of health status developed by the EuroQol Group in order to provide a simple measure of health for clinical and economic appraisal. It measures 5 dimensions: mobility, self-care, usual activities, pain/discomfort and anxiety/depression. Each of the dimensions is divided into 5 levels of perceived problems ranging from 1 (no problem) to 5 (extreme problem).

For each patient, a 5-digit score is obtained by combining each of the 5 dimensions. For example, score 11111 indicates no problems on any of the 5 dimensions, while score 12345 indicates no problems with mobility, slight problems with washing or dressing, moderate problems with doing usual activities, severe pain or discomfort and extreme anxiety or depression. For each patient, the EQ-5D-5L index, ranging from -0.594 to 1.0 is derived from this score using the United Kingdom population-based scoring ([4](#), [5](#)).

In addition, the EQ-5D has a single VAS to evaluate perceived current health. The VAS is scored between 0 and 100 by using the values indicated on the VAS where the patient has placed their mark, or by using the value written by the patient.

For index and VAS, missing data will not be imputed. Ambiguous values (eg, 2 boxes are ticked for a single dimension) on the health state/index score are treated as missing.

- Change in efficacy endpoints (mRSS, HAQ-DI, VAS from SHAQ, observed FVC, % predicted FVC, observed DLco [corrected for hemoglobin], % predicted DLco [corrected for hemoglobin], UCLA SCTC GIT 2.0 score, TJC28, digital ulcer count, CRISS, and EQ-5D-5L index and VAS) from baseline to Week 35 (up to end of follow-up period) and proportion of patients with improvement in mRSS of at least 20%, 40% and 60% from baseline to Week 35.

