2.4.4.4 Analyses of exploratory efficacy endpoints

All exploratory endpoints are described in [Section 2.1.4](#) and will be analyzed using the ITT population unless otherwise specified.

Change in continuous exploratory efficacy endpoints from baseline to Week 24 will be analyzed using the same MMRM model as for the primary and continuous secondary efficacy endpoints. Specifically, the model will contain fixed categorical effects of treatment group, randomization strata (as per IRT), time point, randomization strata-by-time point interaction and treatment-by-time point interaction, as well as the continuous fixed covariates of corresponding baseline value and baseline-by-time point interaction. All post-baseline data available from Week 4 to Week 24 analysis windows will be included in the analysis, regardless of adherence to treatment. Missing data will be accounted for by the MMRM. This model will provide baseline adjusted LSmeans estimated at Week 24 in both treatment groups with their corresponding 95% CIs. The SAR156597 to placebo differences of these estimates will be provided with its corresponding 95% and 90% CIs and p-value.

Change in continuous exploratory efficacy endpoints from baseline to Week 35 will be analyzed using the same model. All post-baseline data available from Week 4 to Week 35 analysis windows will be included in the analysis, regardless of adherence to treatment.

2.4.4.4.1 mRSS

Responder rates (proportion of patients with an improvement from baseline in mRSS of at least 20%, 40% and 60%) at Week 24 and Week 35 will be analyzed using a logistic regression with the categorical effects of treatment group and randomization strata (as per IRT) and the continuous effect of mRSS at baseline. This model will provide the SAR156597 to placebo odds ratio estimate and its 95% and 90% confidence intervals. The p-value will be obtained from the

Wald Chi-square test. Patients with missing value at Week 24, respectively Week 35, will be considered as non-responders. Cumulative distribution function (CDF) graphs will be also presented (percentage of patients according to the relative improvement from baseline in mRSS) at W24 and W35.

Furthermore, the change from baseline to Week 35 will be analyzed using the MMRM model described in [Section 2.4.4.4](#).

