2.4.4.4.7 HAQ-DI

Change in HAQ-DI total score from baseline to Week 35 will be analyzed using the MMRM model described in [Section 2.4.4.4](#).

CDF graphs will be also presented (percentage of patients according to the relative improvement from baseline in HAQ-DI) at Week 24 and Week 35.

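### Relative improvement is a poor metric for the exploratory CDF graphs of HAQ-DI, the SHAQ VAS and EQ-5D-5L, because it is undefined at a zero baseline, unstable near zero and, for the EQ-5D-5L index, can reverse direction

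*SAP*

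**What the plan says.** The SAP plans CDF graphs at Weeks 24 and 35 for four groups of measures, all on the same metric:

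- **mRSS (2.4.4.4.1):** "percentage of patients according to the relative improvement from baseline in mRSS".
- **Each SHAQ VAS (2.4.4.4.2):** "percentage of patients according to the relative improvement from baseline in VAS".
- **EQ-5D-5L index and VAS (2.4.4.4.6):** "percentage of patients according to the relative improvement from baseline in EQ-5D-5L value".
- **HAQ-DI (2.4.4.4.7):** "percentage of patients according to the relative improvement from baseline in HAQ-DI".

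The scale ranges are given elsewhere in the SAP. Section 2.1.4 describes the EQ-5D-5L index as "ranging from -0.594 to 1.0" and says of the EQ VAS: "The VAS is scored between 0 and 100 by using the values indicated on the VAS". The same section scores each SHAQ VAS from 0 to 100. Section 2.1.3.2 puts HAQ-DI between 0, meaning no impairment, and 3.

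The SAP gives no formula for relative improvement, no rule for a zero or negative baseline, and no denominator for these graphs. Among these measures, protocol 7.2 sets entry limits only for mRSS: E 03 excludes scores below 10 or above 35. SAP Appendix B lists the CDFs but names no metric.

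**The concern.** A relative change works only when the baseline is positive and not close to zero. The mRSS entry limit secures that for eligible patients. Nothing secures it for the other scales.

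A patient with no functional impairment has a HAQ-DI of 0, and a patient without digital ulcers could mark 0 on the ulcer VAS. Neither has a relative change to plot. On both instruments lower is better, so a patient at 0 cannot improve. If these patients are left out, the graph loses people whose only possible change is for the worse. The EQ-5D-5L index raises a further question of direction when its baseline is below zero.

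What is at stake is how individual change is displayed. Protocol 9.1.3 and 11.4.2.2 plan responder analyses based on a minimally important change for HAQ-DI, the SHAQ VAS and EQ-5D-5L. The SAP's analysis sections do not carry these, and its list of modifications (1.6) does not mention them. Within the SAP, these CDFs are therefore the planned view of individual change on those instruments.

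**Working it through.** **Plan's own figures.** The plan states no figure for these graphs. Its sample size reproduces: n per arm = 2 × (7/3.6)² × (1.645 + 0.842)² ≈ 46.8, so 47, with 80.2% power by the normal approximation. It plays no part in this point.

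**Inputs.** The ranges are those in SAP 2.1.3.2 and 2.1.4: EQ-5D-5L index -0.594 to 1.0, HAQ-DI 0 to 3, SHAQ VAS and EQ VAS 0 to 100. The patient values below are illustrations inside those ranges, not trial data.

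**Formula.** The SAP gives none, so I assume the usual one with a signed baseline b and follow-up f:

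- higher is better (EQ-5D-5L): 100 × (f − b)/b
- lower is better (HAQ-DI, SHAQ VAS): 100 × (b − f)/b

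**Results.** Positive percentages mean improvement.

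| Scale | Baseline | Follow-up | True change | Relative improvement |
|---|---|---|---|---|
| EQ-5D-5L index | -0.10 | 0.10 | better by 0.20 | 0.20/(-0.10) = -200% |
| EQ-5D-5L index | -0.10 | -0.30 | worse by 0.20 | -0.20/(-0.10) = +200% |
| EQ-5D-5L index | -0.594 | 1.0 | better by 1.594 (the maximum) | 1.594/(-0.594) = -268% |
| EQ-5D-5L index | 0 | 0.08 | better by 0.08 | undefined |
| EQ-5D-5L index | 0.02 | 0.10 | better by 0.08 | 0.08/0.02 = 400% |
| EQ-5D-5L index | 0.60 | 0.68 | better by 0.08 | 0.08/0.60 = 13.3% |
| HAQ-DI | 0 | 0.5 | worse by 0.5 | undefined |
| HAQ-DI | 0.125 | 0.25 | worse by 0.125 | -0.125/0.125 = -100% |
| HAQ-DI | 1.5 | 1.625 | worse by 0.125 | -0.125/1.5 = -8.3% |
| SHAQ VAS | 0 | 40 | worse by 40 | undefined |
| SHAQ VAS | 2 | 40 | worse by 38 | -38/2 = -1900% |

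**Which scale has which problem.**

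- *Undefined at zero:* possible in principle on all these scales, and most plausible for HAQ-DI and the SHAQ VAS. A zero on the EQ VAS means the worst imaginable health, so it is less likely, and such a patient could only stay or improve.
- *Unstable near zero:* all these scales.
- *Reversed direction:* the EQ-5D-5L index only, since no other scale can be negative.

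**Dividing by |b| instead.** This gives +200% and -200% for the first two rows, so the direction is right. It leaves every zero baseline undefined and every near-zero result unchanged.

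**Absolute change.** Every row has a value with the right direction, as the "true change" column shows.

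**How many patients.** The documents give no baseline distribution. Assumed shares of 1%, 5%, 10%, 20% and 30% with a zero or negative baseline on a given scale, multiplied by 94, give about 1, 5, 9, 19 and 28 patients.

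**The case against.** Several arguments limit the point, and most of them stand.

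- **A reader might infer that the SAP, as written, plots the sickest EQ-5D-5L patients as worsening when they improve.** The text does not go that far. It gives no formula, and the reversal follows only from dividing by the signed baseline. Division by the absolute baseline also fits the wording and keeps the direction, though it does nothing for baselines at or near zero.
- **A reader might infer that a secondary endpoint result is compromised, because HAQ-DI is one.** It is not. The secondary analysis of HAQ-DI is the MMRM on change from baseline (2.4.4.2); the CDF sits in the exploratory section. The SHAQ VAS and EQ-5D-5L are likewise analysed by MMRM on change (2.4.4.4). No test is attached to the graphs.
- **The 0.125 step on HAQ-DI is not the smallest change possible.** The score is averaged over the answered domains, of which there may be six, seven or eight. A step of 1/8 applies when all eight are answered. The resulting -100% is defined and has the right sign, so it illustrates instability, not error.
- **Loss of patients at zero is inferred.** The denominator is not stated. The value cannot be computed, however, so these patients cannot be placed on the axis without a rule that the SAP lacks.
- **A formula with a handling rule could serve instead.** It would remove the ambiguity, but any rule for zero would be arbitrary, and near-zero baselines would still stretch the axis.

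**Conclusion.** The point holds as a minor flaw in the metric for descriptive exploratory graphs. Relative improvement is undefined at a zero baseline and unstable near zero for the SHAQ VAS, HAQ-DI, the EQ-5D-5L index and the EQ VAS. These failures follow from the SAP's own score ranges and the absence of any entry limit on these scales. For the EQ-5D-5L index alone, a negative baseline also reverses direction, on the assumption that the signed baseline is the divisor.

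The number of patients affected cannot be established from the documents and could be none; the range of 1 to 28 rests entirely on assumed shares. The mRSS CDF is sound for eligible patients. The primary analysis, the MMRM results and the sample size do not change.

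**What to change.** In SAP 2.4.4.4.2, 2.4.4.4.6 and 2.4.4.4.7:

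- Define the CDFs on absolute change from baseline, with the direction of improvement labelled.
- State the denominator, for example patients with both a baseline and a value at the time point, and report the number without both.
- Mark the 0.08 threshold from protocol 11.4.2.2 on the EQ-5D-5L index graph. An absolute scale makes that threshold readable; a relative one does not.

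Keep relative improvement for the mRSS CDF in 2.4.4.4.1, where E 03 requires a baseline of at least 10. Appendix B states no metric, so it needs only a clarifying phrase.

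The cost is a few lines of SAP wording. The programming effort is the same, no new data are needed, and the graphs would be on the same scale as the MMRM analyses.

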2.4.4.4.7 HAQ-DI

Change in HAQ-DI total score from baseline to Week 35 will be analyzed using the MMRM model described in [Section 2.4.4.4](#).

CDF graphs will be also presented (percentage of patients according to the relative improvement from baseline in HAQ-DI) at Week 24 and Week 35.

2.4.4.4.8 FVC

Due to the non-normality of the distribution of % predicted FVC, the change from baseline at Week 24, respectively Week 35, will be analyzed using a rank-based analysis of covariance (rank analysis of covariance [ANCOVA]) model adjusted for baseline and stratified on randomization stratum (as per IRT). This model will use the ranks of absolute change from baseline to Week 24 (respectively Week 35) in % predicted FVC as the outcome and the ranks of baseline % predicted FVC as a covariate stratified on the stratification factor (with/without ILD). In case of ties, the mean of the corresponding ranks will be assigned.

The ranking will be done within each stratum of the stratification factor (with/without ILD) in ITT population (both treatment groups combined).

- Missing data due to death will be ranked based on a time-to-death, with shortest time until death as the worst (lowest) rank (from 1 to $n_{\text{stratum, death}}$).
- Absolute change from baseline at Week 24 (respectively Week 35) in % predicted FVC values will be calculated from Week 24 (respectively Week 35) % predicted FVC values and then ranked (from $n_{\text{stratum, death}} + 1$ to n_{stratum}).
- Standardization of ranks using SAS PROC RANK.

Furthermore, the adjustment on baseline % predicted FVC covariate will be done. The residuals from the linear regression of response ranks on baseline ranks will be calculated within each stratum of the stratification factor (with/without ILD).

Finally, treatment effect will be tested using the residuals as scores. The active treatment group will be compared to placebo using a Mantel-Haenszel mean score chi-square test at a one-sided Type-I error level of 5%. This test will be stratified on the stratification factor.

In case of more than 20% of missing data on the % predicted FVC value at Week 24, missing data will be imputed following methods described in [Section 2.5.2](#). Otherwise, the data will not be imputed.

Furthermore, the change in observed FVC from baseline to Week 35 will be analyzed using the MMRM model described in [Section 2.4.4.4](#).

The number of patients with an absolute decreased % predicted FVC from baseline at W24 superior or equal to 5% and respectively 10% will be presented by treatment group.

2.4.4.4.9 DLco

Same rank ANCOVA as for % predicted FVC will be done for the change in % predicted DLco from baseline at Week 24 and Week 35, using % predicted DLco as the outcome and the ranks of baseline % predicted DLco as a covariate stratified on the stratification factor.

Furthermore the change in observed DLco (corrected for hemoglobin) from baseline to Week 35 will be analyzed using the MMRM model described in [Section 2.4.4.4](#).

The number of patients with an absolute decreased % predicted DLCO from baseline at W24 superior or equal to 5% and respectively 10% will be presented.

2.4.4.4.10 CRISS

The distribution of the predicted probability of improving obtained using the CRISS at Week 24 and Week 35 will be compared between SAR156597 and the placebo group using a Van Elteren's test stratified on randomization strata.

In case of more than 20% of missing data on the CRISS value at Week 24, missing data will be imputed following methods described in [Section 2.5.2](#). Otherwise, the data will not be imputed.

In addition, rate of patients for whom the predicted probability of improving obtained using the CRISS at Week 24 and Week 35 is $\geq 60\%$ will be provided.

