The distribution of the predicted probability of improving obtained using the CRISS at Week 24 and Week 35 will be compared between SAR156597 and the placebo group using a Van Elteren's test stratified on randomization strata. Methods to handle missing data will be described in the SAP. In addition, rate of patients for whom the predicted probability of improving obtained using the CRISS at Week 24 and Week 35 is $\geq 60\%$ will be provided. To assist in interpreting the clinical meaningfulness of any differences in group-level mean change for SHAQ (HAQ-DI and VAS) and EQ-5D-5L (index value and VAS), individual-level change will be assessed. For this, patients will be categorized as "responders" and "non-responders" according to whether they have achieved a threshold of change considered to be meaningful (the MIC). Patients who improve by \geq the MIC will be considered as clinically important responders (CIRs). As there is little data to support an accepted MIC value for HAQ-DI (20) and the SHAQ VAS assessments in dcSSc, estimates will be empirically-derived from within this study using both distribution-based and anchor-based methods. Distribution-based methods will include one-half a SD and 1 standard error of measurement (SEM) of the baseline score (22, 23, 24). Anchor-based methods will use the EQ-5D index value in which the magnitude of change in the HAQ-DI and the SHAQ VASs among patients who noted at least a 0.08 improvement in their current health status (0-1 scale) will define the MIC (25, 26, 27).

For the EQ-5D-5L, CIRs will be defined by an MIC of ≥ 0.08 in the index value. CIRs on the EQ-5D VAS will be defined using the same methods as for the HAQ-DI and SHAQ VASs (ie, 0.5SD, 1SEM, EQ-5D index value as an anchor).

The proportion of patients classified as CIRs will be assessed within the ITT sample. Patients without data at the relevant time point will be classified as non-responders. Comparison between groups on responder rates will be performed as described above using a logistic regression.

Please refer to [Section 9.1.2](#) for the secondary efficacy endpoints.

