The digital ulcer count corresponds to the sum of active or new plus indeterminate/healing digital ulcers secondary to SSc (see [Appendix I](#)).

- CRISS.

The Composite Response Index for Diffuse Cutaneous Systemic Sclerosis (CRISS) tool summarizes the changes in the clinical and patient-reported outcomes using a single composite score that reflects the probability that the patient with dcSSc has improved.

CRISS is obtained in a 2-step process as described below.

Step 1: Patients who develop new or worsening of cardiopulmonary and/or renal involvement due to SSc are considered as not improved (irrespective of improvement in other core items) and assigned a probability of improving equal to 0.0. Specifically if a subject develops any of the following:

- New scleroderma renal crisis.
- Decline in FVC% predicted $\geq 15\%$ (relative), confirmed by another FVC% within a month, high resolution computer tomography (HRCT) to confirm ILD (if previous HRCT of chest did not show ILD) and FVC% predicted below 80% predicted*.
- New onset of left ventricular failure (defined as left ventricular ejection fraction $\leq 45\%$) requiring treatment*.
- New onset of Pulmonary Arterial Hypertension (PAH) on right heart catheterization requiring treatment*. PAH is defined as mean pulmonary artery pressure ≥ 25 mm Hg at rest and an end-expiratory pulmonary artery wedge pressure ≤ 15 mm Hg and a pulmonary vascular resistance > 3 Wood units.

*Attributable to SSc

Step 2: For the remaining patients, Step 2 involves computing the predicted probability of improving for each subject using the following equation (equation to derive predicted probabilities from a logistic regression model):

$$\frac{\exp(-5.54-0.81*\Delta\text{MRSS}+0.21*\Delta\text{FVC\%}-0.40*\Delta\text{Pt-glob}-0.44*\Delta\text{MD-glob}-3.41*\Delta\text{HAQ-DI})}{1+\exp(-5.54-0.81*\Delta\text{MRSS}+0.21*\Delta\text{FVC\%}-0.40*\Delta\text{Pt-glob}-0.44*\Delta\text{MD-glob}-3.41*\Delta\text{HAQ-DI})}$$

ΔmRSS indicates the change in mRSS from baseline, $\Delta\text{FVC\%}$ denotes the change in FVC% predicted from baseline, $\Delta\text{Pt-glob}$ indicates the change in patient global assessment (as per Likert scale), $\Delta\text{MD-glob}$ denotes the change in physician global assessment (as per Likert scale) (see [Appendix G](#)), and $\Delta\text{HAQ-DI}$ is the change in HAQ-DI. All changes are absolute change ($\text{Time}_2 - \text{Time}_{\text{baseline}}$).

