2.5.2 Data handling conventions for efficacy variables

Handling of CRISS missing data

Two different methods will be used to impute CRISS missing data, depending on the nature of the missing item.

If the missing item at a given time-point relates to organ involvement (Step 1 of CRISS derivation):

- If there was already an organ involvement at a previous post-baseline time-point (CRISS already evaluated as 0 at a previous time point), CRISS will be imputed the value of 0.
- Otherwise, if at the current time-point, one organ has worsened (CRISS evaluated as 0 due to new or worsening of another organ for which the evaluation is non missing), CRISS will be imputed the value of 0.
- Otherwise, if no other organ has worsened, as such an event should have been classified as a serious adverse event, it is assumed that no organ had worsened otherwise the event would have been recorded, so CRISS will be derived using Step 2. Each missing component (FVC, DLco, mRSS, PT-glob, MD-glob and HAQ-DI) at Week 24 will be imputed using the method explained below.

Handling of FVC, DLco and CRISS missing data

In order to impute the FVC, DLco and CRISS missing data at Week 24, the following steps will be performed:

- Patients in active arm and taking treatment at Week 24 (treatment discontinuation is defined for this analysis as last injection + 7 days): Missing values at Week 24 will be imputed using a model estimated from the subset of patients in the active arm who completed the 24-week treatment period and with a Week 24 value. The imputation model will be based on a MMRM with fixed categorical effect of stratification (as per IRT, with/without ILD) and repeated categorical effect for time point (baseline, Week 4 (except for % predicted DLco and % predicted FVC), Week 8 (except for % predicted DLco and % predicted FVC), Week 12 and Week 24). Parameters will be estimated with the Newton-Raphson algorithm, an unstructured covariance matrix will model the within-patient errors, and the denominator degrees of freedom will be estimated using Kenward-Roger's approximation. Missing values at Week 24 will be imputed using the Empirical Best Linear Unbiased Prediction (EBLUP).
- Other patients (patients in active arm and not taking treatment at Week 24; or patients in placebo arm): Missing values at Week 24 will be imputed similarly but using a model estimated from the subset of patients in the placebo arm who completed the 24-week treatment period and with a Week 24 value.

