2.5.3 Missing data

For categorical variables, patients with missing data are not included in calculations of percentages unless otherwise specified. When relevant, the number of patients with missing data is presented.

Handling of computation of treatment duration if investigational medicinal product end of treatment date is missing

For the calculation of the treatment duration, the date of the last dose of IMP is equal to the date of last administration reported on the end-of-treatment case report form page. If this date is missing, the exposure duration should be left as missing.

The last dose intake should be clearly identified in the case report form and should not be approximated by the last returned package date.

Handling of medication missing/partial dates

No imputation of medication start/end dates or times will be performed. If a medication date or time is missing or partially missing and it cannot be determined whether it was taken prior or concomitantly, it will be considered as prior, concomitant, and post-treatment medication.

Handling of adverse events with missing or partial date/time of onset

Missing or partial adverse event onset dates and times will be imputed so that if the partial adverse event onset date/time information does not indicate that the adverse event started prior to treatment or after the treatment-emergent adverse event period, the adverse event will be classified as treatment-emergent. No imputation of adverse event end dates/times will be performed. These data imputations are for categorization purpose only and will not be used in listings. No imputation is planned for date/time of adverse event resolution.

Handling of adverse events when date and time of first investigational medicinal product administration is missing

When the date and time of the first IMP administration is missing, all adverse events that occurred on or after the day of randomization should be considered as treatment-emergent adverse events. The exposure duration should be kept as missing.

The last dose intake should be clearly identified in the case report form and should not be approximated by the last returned package date.

Handling of missing assessment of relationship of adverse events to investigational medicinal product

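### Read literally, the SAP applies a CRISS of 0 already fixed by an organ event to a missed Week 24 visit only if more than 20% of CRISS values are missing

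*SAP*

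**What the plan says.** **Step 1 (SAP 2.1.4; the same rule is in Protocol 9.1.4.10).** Patients who develop renal crisis, a confirmed FVC decline, left ventricular failure or PAH as defined there "are considered as not improved (irrespective of improvement in other core items) and assigned a probability of improving equal to 0.0". No visit is named, and nothing is said about a later missed visit.

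**Analysis (SAP 2.4.4.4.10).** CRISS at Week 24 and Week 35 is compared by a Van Elteren "test stratified on randomization strata", and the rate of patients at 60% or above is reported. The rule on missing values points to the methods of 2.5.2: "In case of more than 20% of missing data on the CRISS value at Week 24, missing data will be imputed following methods described". When that condition is not met: "Otherwise, the data will not be imputed".

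**Methods (SAP 2.5.2).** "Two different methods will be used to impute CRISS missing data, depending on the nature of the missing item". The first organ rule covers a patient whose organ event was scored at an earlier visit: "CRISS already evaluated as 0 at a previous time point), CRISS will be imputed the value of 0".

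**Other relevant text.** SAP 2.5.3 sets the default for categorical variables: "patients with missing data are not included in calculations of percentages unless otherwise specified". Protocol 11.4.2.2 defers the matter: "Methods to handle missing data will be described in the SAP". No section exempts the Step 1 zero from the 20% condition.

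**The concern.** Once a Step 1 event has occurred, the CRISS value is known and no Week 24 component can change it. A threshold on the overall amount of missing data is a reasonable gate for model-based imputation of unknown values. It is not a reasonable gate for a value already determined. If it is applied there, whether a known worst outcome counts depends on how many other patients happen to be missing.

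The values at risk are the lowest ranks, and their number may differ by arm. Losing them helps whichever arm has more of them.

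The SAP treats comparable cases differently. In 2.4.4.4.8, deaths receive the lowest ranks for % predicted FVC within the ranking itself. In 2.4.4.4.1, a missing mRSS counts as non-response in the 20%, 40% and 60% responder analyses, with no threshold.

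**Working it through.** **1. Sample size.** The plan gives no figure for CRISS, so only N is needed. Power for mRSS with 47 per arm, difference 3.6, SD 7 and one-sided 5%: 3.6 / (7 × √(2/47)) = 2.493; 2.493 − 1.645 = 0.848; Φ(0.848) = 0.802. The stated 80% reproduces and N = 94 stands. The CRISS point does not affect it.

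**2. Where the trigger falls.** 0.20 × 94 = 18.8. 18/94 = 19.1% does not exceed 20%; 19/94 = 20.2% does. Up to 18 missing values are therefore left unimputed. The SAP does not say whether the share is overall or per arm. Overall is assumed here; per arm, 0.20 × 47 = 9.4, so up to 9. The plan expects 10% treatment discontinuation (about 9 of 94) with visits continuing, so staying below the trigger is plausible.

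**3. Who is affected.** SAP Table 3 sets the Week 24 CRISS window at days 127 to 207. An event scored inside it gives a Week 24 value of 0 under Step 1. The gap therefore mainly concerns survivors with an event before day 127 and no CRISS value in the window. Table 3 also has no CRISS window before day 71, so a patient with an earlier event and no later visit may have no previous time point holding a 0. The 2.5.2 rule might then miss that patient even when triggered.

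**4. The rate at 60% or above (assumed counts).** Suppose 18/47 active and 12/47 placebo patients reach 60%, and 1 active and 4 placebo patients have an earlier event and no Week 24 CRISS.
- Zeros kept: 18/47 − 12/47 = 38.3% − 25.5% = 12.8 points.
- Zeros left out: 18/46 − 12/43 = 39.1% − 27.9% = 11.2 points.

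**5. The Van Elteren test (simulation, assumed inputs).** 4,000 runs, 47 per arm, two near-equal strata and no treatment difference among patients without an event. The CRISS linear predictor uses the plan's intercept and mRSS coefficient, with an assumed mean mRSS improvement of 4 (SD 7) and a normal term (SD 3) for the other components. Positive Z favours active.

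| Event patients without Week 24 CRISS, active / placebo | Mean Z, scored 0 | Mean Z, left out | Active rate, scored 0 | Active rate, left out |
|---|---|---|---|---|
| 3 / 3 | −0.03 | −0.04 | 31.4% | 33.5% |
| 1 / 5 | 0.70 | −0.01 | 33.0% | 33.7% |
| 5 / 1 | −0.72 | −0.01 | 30.2% | 33.8% |
| 8 / 2 | −1.07 | −0.01 | 28.0% | 33.8% |

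When the zeros are left out, the imbalance in organ events disappears from the test, in whichever direction it ran. When events are balanced, the test statistic hardly moves.

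**The case against.** A reader might infer that the SAP definitely drops patients with known organ failure. The documents do not support that as a settled fact, for three reasons.

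- Step 1 names no visit. If an event fixes CRISS at 0, the Week 24 value can be regarded as derived, hence not missing, and the 20% condition never reaches it. This reading would make the first organ rule in 2.5.2 redundant. But the second organ rule is redundant in the same way: it labels as imputed a 0 that Step 1 already gives from another organ at the same visit. The label alone therefore does not settle the matter.
- The organ rule in 2.5.2 applies at any given time point, whereas the model-based method is tied to Week 24. The 20% sentence can be read as aimed at the model only, since 2.4.4.4.8 uses the same sentence for % predicted FVC, where no organ rule applies. On that reading the organ rule also covers Week 35.
- The SAP says only that data are not imputed. Exclusion from the rank test is the ordinary consequence, but it is inferred.

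The scale is also limited. Patients who stop treatment are asked to attend Week 24 (Protocol 10.3.4), the window spans 81 days, and unscheduled visits may supply a value (SAP 2.5.5). Five affected patients, as in step 4 of the working, would be more than half of about 9 expected discontinuations. Organ events remain visible elsewhere: 2.5.2 expects them to be serious adverse events, and the overall responder definition in 2.4.4.4.1 requires no CRISS event.

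All of this stands. It lowers the certainty and the size. It does not remove the problem, because no section exempts the Step 1 zero and two programmers could reasonably code it differently.

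**Conclusion.** The point holds as a conflict or ambiguity between SAP 2.1.4, 2.4.4.4.10 and 2.5.2. On the literal reading, a value already fixed by Step 1 is lost when 18 or fewer of 94 Week 24 CRISS values are missing, for survivors with an event before day 127 and no CRISS value in days 127 to 207. At Week 35 the SAP states no trigger, so the handling there is open.

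The documents give no organ-event rate. The number affected is unknown and probably small, and the 1.6-point change (12.8 − 11.2) and the simulated Z values rest on assumed counts. A reader might also infer a bias towards SAR156597; the documents do not support a direction, since it depends on which arm has more such patients. Only an exploratory endpoint is touched, with p-values for description (SAP 2.4.4.3). The primary and secondary analyses are unaffected.

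**What to change.** Amend three SAP sections:

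- **2.1.4:** state that any Step 1 event between baseline and a time point sets CRISS to 0 at that and every later time point, including Week 35, whether or not later components are observed and whatever the share of missing data.
- **2.5.2:** move the organ-event zeros out of the imputation methods and refer to that derivation.
- **2.4.4.4.10:** keep the 20% trigger for missing Step 2 components only, counted after the Step 1 zeros are assigned. Say whether the share is overall or per arm, and what applies at Week 35.

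The cost is wording and a small programming change. Step 1 is already assessed at Weeks 12, 24 and 35, so no new data are needed.
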